
**Evaluation and Refinement of OPTIMAL (Aim 1).** After the intervention protocol and training materials are developed, we conducted one focus group of NH stakeholders including leadership, staff, and families to prioritize the multiple mealtime difficulties identified from literature and to understand the acceptability of the OPTIMAL intervention following an interview guide. The focus

group was audio-recorded, and facilitated by the PI experienced in conducting focus group interviews. Data obtained were analyzed and used to refine the intervention protocol and training materials before pilot testing.

**Inclusion/Exclusion Criteria (Aim 2 and 3).** Participants including staff, residents, and families were recruited from nursing homes. Staff are eligible if they are 18 years old or above, English speaking, a permanent facility employee, provide informed consent, and provide direct mealtime care for a resident participant at least twice a week over the previous month. Families are eligible if they are 18 years old or above, English speaking, a family member of the resident who is living at the NH study site at the time of the study, having experiences of delivering mealtime care to their resident family members, and providing informed consent.

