### **Feasibility, Fidelity, and Usefulness Data (Aim 2)**

**Feasibility of OPTIMAL.** Descriptive data on identification, recruitment, consent, and retention of staff, resident, and family participants will be gathered to assess intervention feasibility (see Appendix 5). In addition to the number of participants screened and eligible for the study, the recruiter will track reasons for those unwilling to participate in the study, and whether that is specifically related to video recording and/or OPTIMAL intervention. We will record the number of participants deemed not eligible and reasons for ineligibility as a basis for planning future trials of OPTIMAL. The length of time it takes to obtain assents/consents from residents, staff, families, and LARs, as well as the number of families and LARs who don't mail back their written consent within expected time period (i.e., 2 weeks after they receive blank consent forms by mail) will be tracked. Families/LARs will be contacted to determine barriers to return of consents and how processes could be changed to facilitate timely return of consent. We will track the number of residents and staff requiring rescheduling of video recording sessions and the reasons for rescheduling. We will track the number of resident and staff participants who withdraw at various time points (e.g., before, during, and after T1, T2, and T3), and those who withdraw will be contacted to determine reasons for withdrawal and how process could be changed to facilitate retention.

**Fidelity of OPTIMAL.** We will assess three aspects of fidelity: 1) delivery of treatment, tracking staff attendance at the group or individual training sessions using a checklist, 2) receipt of treatment, indicated by a total test score of  $\geq 75\%$  on the staff PCMC-related knowledge & self-efficacy test post-training with or without booster sessions (we will track the number of group or individual booster sessions offered in each NH), and 3) enactment of treatment skills, including quality of staff engagement assessed by the 19-item Mealtime Engagement Scale developed

by the PI with evidence of reliability and validity (each item is scored on 0-3, total score range: 0-57, higher score = higher quality of engagement).

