### **Statistical Analysis Plan.**

**Develop, evaluate, and refine OPTIMAL intervention protocol and training materials (Aim 1).** We developed OPTIMAL through systematic integration of four PCMC principles, our prior work on multilevel facilitators and barriers to *engaging residents in eating*, and our systematic review of mealtime difficulties and targeted behavioral strategies. We integrated evidence from literature and our prior work to develop the intervention protocol and training materials, addressing resident mealtime difficulties, targeted PCMC strategies, and establishment of individualized PCMC plans. We conducted focus group interviews of staff participants on the acceptability and appropriateness of the intervention protocol and training materials before pilot testing. Based on

staff overall comments, the OPTIMAL components were highly evaluated as timely and fit to the needs of care practice. Data obtained were used to refine the intervention protocol and training materials before pilot testing.

**Determine feasibility, fidelity, and usefulness of OPTIMAL (Aim 2).** We described feasibility data on participant identification, recruitment, consent and retention, including the number of and reasons for participants' ineligibility, unwillingness to participate, not consenting/assenting, not returning written consent within expected time period, and attrition/withdrawal. We used this information to refine study procedures for a future larger trial to facilitate recruitment and retention. We described treatment fidelity, including staff attendance at training sessions and staff PCMC-related knowledge scores pre- and post-training. Audio-recorded focus group interviews from staff (usefulness) were transcribed and coded. We extracted codes using open coding (using staff's own words) to address the usefulness and areas of refinement of OPTIMAL.

**Describe resident outcomes (Aim 3).** We described distributions of resident eating performance, mealtime challenging behaviors including resistive behaviors and functional impairments, intake success rate, and BMI using appropriate descriptive statistics (mean, median, mode, range, variance, SD, percentile and quartile ranks, n, %) over time. These data were used to inform estimates of effect sizes for sample size calculation in a future trial.

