**Expected Outcomes and Impact for Future Trials.** *Using mixed methods, qualitative and quantitative data will be collected and analyzed to refine OPTIMAL intervention protocol, training materials, and study procedures, and to understand its feasibility, fidelity, and usefulness. Data obtained from this pilot trial will provide five critical pieces of information for a future larger efficacy trial. They are:* 1) refined OPTIMAL intervention protocol and training materials with preliminary evidence of feasibility, fidelity, and usefulness; 2) refined study procedures for recruitment, retention, data collection, and recording and behavioral coding of videos; 3) evidence of feasibility for a two-group parallel cluster RCT design with three repeated measures (baseline, 6- & 12-weeks post baseline); 4) effect size estimates of resident outcomes for sample size calculation; and 5) videotaped observations collected in this study to be used in future staff training sessions to illustrate OPTIMAL care skills.

**Limitations.** As a pilot RCT, a small sample of staff and residents from 4 NHs will be enrolled. This is a logical first step to develop and test a new behavioral intervention, prior to a large-scale efficacy trial.

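### The pilot promises feasibility evidence for a two-group cluster RCT, but its Design section is single-group and the supplied text counts no nursing homes

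*Combined protocol and SAP*

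**What the plan says.** The paragraph on Expected Outcomes and Impact for Future Trials lists five things the pilot data will supply to a later efficacy trial. The third is "evidence of feasibility for a two-group parallel cluster RCT design with three repeated measures".

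The Design section describes the pilot as single-group, measured at baseline, 6 weeks and 12 weeks. It mentions no allocation and no control arm. Other places differ: Aim 3 under Objectives refers to two treatment groups, the paragraph on usefulness mentions an education control group, and the Limitations paragraph calls the study a pilot RCT.

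On feasibility data, the Aim 2 section says: "Descriptive data on identification, recruitment, consent, and retention of staff, resident, and family participants will be gathered to assess intervention feasibility". On screening and refusal, it has a sentence that begins: "In addition to the number of participants screened and eligible for the study, the recruiter will track reasons for those unwilling to participate in the". On attrition: "We will track the number of resident and staff participants who withdraw at various time points". The SAP for Aim 2 follows the same line: "We described feasibility data on participant identification, recruitment, consent and retention".

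On homes, the eligibility text says "Participants including staff, residents, and families were recruited from nursing homes", and the Limitations paragraph says "a small sample of staff and residents from 4 NHs will be enrolled".

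**The concern.** A parallel cluster RCT makes demands that a single-group study does not. Clusters must agree to be allocated by chance, some must carry a control condition, and both arms must stay to the last measurement. The third product says the pilot will bear on that design. If the Design section is right, the pilot has no allocation and no comparison arm, so those elements are never put to the test.

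The second gap is the unit of counting. The cluster in the later trial is evidently the nursing home, yet every recruitment and retention item in the supplied text concerns people. Someone planning the later trial would want to know how many homes must be approached to enrol one, and how many stay to 12 weeks. The text gives no means of answering either question. It also does not ask for consent, retention, attendance or test-score results by home, so a poor result in one home could be diluted in a pooled figure.

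At stake is a later application citing this pilot as evidence that a randomised cluster design works, when the pilot did not examine it.

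**Working it through.** The plan states no feasibility threshold, sample-size calculation or home-level figure, so there is nothing to reproduce. The check is mainly a comparison of texts, with a short calculation to show what home counts could add.

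**Step 1. Parts of the promised conclusion against what the plan observes**

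| Part of the third product | What the supplied text observes | Supported? |
|---|---|---|
| Three repeated measures | Measurements at T1, T2 and T3; rescheduling and withdrawals tracked | Yes |
| Two-group, parallel | Single group in the Design section; no allocation or control arm there | No |
| Cluster | Staff, residents and families counted; homes not counted | No |
| Randomised | No randomisation procedure in the supplied text; reasons for refusal concern video recording or the intervention, not allocation | No |

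**Step 2. Search for home-level items elsewhere**

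- The feasibility and fidelity section has one per-home count, booster training sessions. That is a fidelity item.
- Home leaders took part in the Aim 1 focus group, but its topics were priorities among mealtime difficulties and acceptability of the intervention.
- The post-T3 focus groups are held per home, but concern staff views of usefulness.
- Appendix 5 (feasibility data) and the Recruitment and Retention Plan are cited but not supplied. The search therefore covers the supplied text only.

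**Step 3. What home-level retention could show**

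Input: n = 4 homes, from the Limitations paragraph. Exact (Clopper-Pearson) 95% limits put 0.025 in each tail.

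- 4 of 4 retained: the lower limit solves p⁴ = 0.025, so p = 0.025^(1/4) = 0.398. Interval 39.8% to 100%.
- 3 of 4 retained: the lower limit solves 4p³(1 − p) + p⁴ = 0.025, giving 0.194. The upper limit solves 1 − p⁴ = 0.025, so p = 0.975^(1/4) = 0.994. Interval 19.4% to 99.4%.
- Chance that all 4 stay is p⁴: 0.7⁴ = 0.24, 0.8⁴ = 0.41, 0.9⁴ = 0.66. A clean record does little to separate these rates.

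**Step 4. What home-level acceptance could show**

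The number of homes approached is not given. As an assumed range, with 4 agreeing:

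| Approached (assumed) | Proportion agreeing | Exact 95% interval |
|---|---|---|
| 5 | 80% | 28% to 99% |
| 8 | 50% | 16% to 84% |
| 10 | 40% | 12% to 74% |
| 20 | 20% | 6% to 44% |

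The observed proportion runs from 20% to 80% depending on a denominator that the supplied text does not record. Counting homes is informative for planning, but with so few homes the result is descriptive.

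**The case against.** The strongest reply has four parts.

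1. **The missing items may sit in documents not supplied.** The feasibility text points to Appendix 5, and recruitment detail is sent to a separate plan. This stands. A reader might infer that the study keeps no home-level records at all; the documents do not support that, because the places where such records would be specified could not be read.

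2. **The promise is left over from a two-group design and would go once the design text is reconciled.** Much of this stands: the single-group design is the main reason the claim fails. But the third product is current text and would have to be changed deliberately. If the design were instead confirmed as two-group, the homes would still be uncounted in the supplied text.

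3. **Aim 2 defines feasibility at participant level, and the SAP matches it.** True, and Aim 2 is not faulted for that. The fault lies in the wider conclusion drawn from those data.

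4. **The intervals argue against collecting home data.** They show that such data cannot estimate a rate with useful precision. They do not show that the number of homes approached, or the reasons for declining, are useless to a planner.

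A reader might also infer that pooled rates will conceal a home that dropped out. That is too strong: withdrawals are tracked by time point and reasons are sought, so a departing home should show up through its participants, and nothing forbids tabulating by home. The narrower point is that by-home reporting is not planned.

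**Conclusion.** The point holds in a limited form. The third product claims feasibility of a two-group cluster RCT, and the single-group study in the Design section cannot supply evidence on allocation, a control arm or differential retention. The lack of home counts in the supplied text is a second, smaller reason. The pilot does support the three-time-point schedule and participant-level recruitment and retention, so a reading that it offers no feasibility evidence would be wrong.

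Two tempting remedies also go too far. Adding home counts would not make the RCT claim good, because even 4 of 4 retained is compatible with a true rate as low as 40%. Asking home leaders whether they would accept control would give stated willingness, not evidence that randomisation works.

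The conclusion rests on these assumptions:

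- The Design section is the operative description of the study.
- The nursing home is the future unit of randomisation. No section names it, but all staff of one home train together, each home has its own champion, and the sample is drawn by home.
- There are 4 homes. That figure comes from the sentence that calls the study a pilot RCT, a label at odds with the Design section, so the intervals are illustrative.

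**What to change.** 1. **Narrow the third product.** Under Expected Outcomes and Impact for Future Trials, claim feasibility of the three repeated measures and of participant-level recruitment and retention in nursing homes. Drop the two-group cluster RCT claim unless homes are actually randomised.

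2. **Reconcile the design descriptions.** The Design section, Aim 3 under Objectives, the usefulness paragraph and the Limitations paragraph should describe one design and state the number of homes.

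3. **Add home-level counts** to the feasibility section and the SAP for Aim 2, if Appendix 5 does not already hold them: homes approached, eligible, agreed, declined with reasons, and retained to T3. Draw them from existing contact records where these exist. Where they do not, say so.

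4. **Report by home.** Give consent, retention, training attendance and test-score figures for each home beside the pooled figure.

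Items 3 and 4 should be labelled descriptive, with no inference about a rate of home acceptance or retention.

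Cost: a narrower claim and a small amount of tabulation, with no new participants or visits. Much of the plan is written in the past tense, so approaches and refusals may not be fully recoverable; the rewording does not depend on them, and by-home tabulation needs only participant data labelled by home.
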